## 6.2. Secondary Endpoints

### 6.2.1. GBS Serotype-Specific IgG GMCs Before and 1 Month After Booster Vaccination

- Analysis population: Evaluable immunogenicity and mITT (provided there is a 10% or more difference with evaluable) populations ([Section 4](#)).

- Analysis time point: Before and 1 month after vaccination.
- Analysis methodology: Descriptive summary statistics.
- Supporting objective: Secondary objective.
- Intercurrent event(s): For participants who discontinue or have major protocol violations, no observations following discontinuation or violation will be used. Results obtained from out-of-window blood draws will also be removed. Missing results will not be imputed.
- GMC of the IgG at each available time point for each serotype will be presented by vaccine group. For each vaccine group, the number of participants with valid assay data (n), GMCs, and associated 2-sided 95% CI will be presented.
- Figures of empirical RCDCs for 1 month after the vaccination time point will be generated separately for each serotype by vaccine group. The figures will be based on the evaluable immunogenicity population only.

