### 1.3. Schedule of Activities (SoA)

The SoA table provides an overview of the protocol visits and procedures. Refer to the [STUDY ASSESSMENTS AND PROCEDURES](#) section of the protocol for detailed information on each procedure and assessment required for compliance with the protocol.

The investigator may schedule visits (unplanned visits) in addition to those listed in the SoA table, in order to conduct evaluations or assessments required to protect the well-being of the participant.

Visit Number	1	2	3
Visit Description	Vaccination	1-Month Follow-up Visit	6-Month Telephone Call
Visit Window (Days) a	Day 1	28-38 Days After Visit 1	160-200 Days After Visit 1
Obtain informed consent	X		
Assign participant number	X		
Record demography	X		
Record medical history	X		
Record vital signs b	X		
Perform physical examination	X		
Perform urine pregnancy test	X		
Record nonstudy vaccine information	X		
Record medication information	X	X c	X c
Review inclusion and exclusion criteria	X		
Measure prevaccination oral temperature	X		
Contraception check d	X		X
Review temporary delay criteria	X		
Review continued eligibility	X		X
Assign container number	X		
Obtain blood sample for immunogenicity assessment e	X (~50 mL)	X (~50 mL or ~150 mL)	
Administer investigational product	X		
Postvaccination observation (30 minutes) and assessment of immediate AEs	X		
Dispense e-diary, thermometer, and measuring device f	X		
Review and/or collect e-diary g		X	

PFIZER CONFIDENTIAL

Visit Number	1	2	3
Visit Description	Vaccination	1-Month Follow-up Visit	6-Month Telephone Call
Visit Window (Days) a	Day 1	28-38 Days After Visit 1	160-200 Days After Visit 1
Record AEs		X	X
Record MAEs and SAEs	X	X	X

Abbreviations: e-diary = electronic diary; MAE = medically attended adverse event.

- a. Day relative to the start of study vaccination (Day 1).
- b. Vital signs include weight, height, sitting blood pressure and pulse rate, respiratory rate, and temperature (oral).
- c. Only concomitant medication taken to treat an adverse event will be recorded in the case report form.
- d. The contraception check is an opportunity to confirm that contraception is used consistently and correctly through the required time period per protocol (3 months after vaccination).

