##### **Secondary (Immunogenicity):**

In participants receiving at least 1 dose of the investigational product and in compliance with the key protocol criteria (evaluable participants):

- GBS serotype-specific IgG GMCs measured before and 1 month after booster vaccination.
- GBS serotype-specific IgG GMCs measured 1 month after booster vaccination stratified by baseline prevaccination status (before the primary vaccination).
- GBS serotype-specific OPA GMTs measured before and 1 month after booster vaccination.

- GBS serotype-specific IgG GMFR from before to 1 month after booster vaccination.
- GBS serotype-specific OPA GMFR from before to 1 month after booster vaccination.

These estimands estimate the vaccine effect in the hypothetical setting where participants follow the study schedules and protocol requirements as directed. Missing serology results will not be imputed, as missing completely at random (MCAR) is assumed. Participants who discontinue or have major protocol deviations before Visit 2 (1 month after receiving the investigational product) will be excluded from the evaluable population in the analysis. Immunogenicity results that are below the lower limit of quantitation (LLOQ) will be set to  $0.5 \times \text{LLOQ}$  in the analysis.

[figure not shown]

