#### 2.1.4. Secondary Estimands

In participants in compliance with the key protocol criteria (evaluable population):

- Group B streptococcus (GBS) serotype-specific IgG GMCs measured before and 1 month after booster vaccination.

This estimand includes the following 4 attributes:

- Population: Evaluable immunogenicity analysis set as defined in [Table 6](#).
- Variable: Antibody concentrations before and 1 month after booster vaccination.
- Intercurrent event(s): For participants who discontinue or have major protocol violations, no observations following discontinuation or violation will be used. Results obtained from out-of-window blood draws will also be removed. Missing results will not be imputed.
- Population-level summary: IgG GMCs.
- GBS serotype-specific opsonophagocytic activity (OPA) geometric mean titers (GMTs) measured before and 1 month after booster vaccination.

This estimand includes the following 4 attributes:

- Population: Evaluable immunogenicity analysis set as defined in [Table 6](#).
- Variable: Antibody titers before and 1 month after booster vaccination.
- Intercurrent event(s): For participants who discontinue or have major protocol violations, no observations following discontinuation or violation will be used. Results obtained from out-of-window blood draws will also be removed. Missing results will not be imputed.
- Population-level summary: OPA GMTs.
- GBS serotype-specific IgG geometric mean fold rise (GMFR) from before to 1 month after booster vaccination.

This estimand includes the following 4 attributes:

- Population: Evaluable immunogenicity analysis set as defined in [Table 6](#).
- Variable: Fold rise from before to 1 month after booster vaccination.
- Intercurrent event(s): For participants who discontinue or have major protocol violations, no observations following discontinuation or violation will be used.

Results obtained from out-of-window blood draws will also be removed. Missing results will not be imputed.

- Population-level summary: GMFR from baseline for IgG concentrations.
- GBS serotype-specific OPA GMFR from before to 1 month after booster vaccination.

This estimand includes the following 4 attributes:

- Population: Evaluable immunogenicity analysis set as defined in [Table 6](#).
- Variable: Fold rise from before to 1 month after booster vaccination.

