**Table 6. Analysis Sets (Populations for Analysis)**

Population	Description
Enrolled	All participants who sign the informed consent document (ICD).
Evaluable immunogenicity	
All participants who:
 
 
• Are eligible (have signed informed consent and met all inclusion/exclusion criteria) and assigned to receive the investigational product in the study;
 
• Have received 1 dose of GBS6 with or without AlPO4 to which they were assigned;
 
• Have a Visit 2 (1 month after vaccination) blood draw for assay testing within 27 to 45 days, inclusive, after vaccine administration;
 
• Have at least 1 valid and determinate assay result at Visit 2 (1 month after vaccination);
 
• Have no major protocol violation as determined by the study clinician.
 
 
The evaluable immunogenicity population will be the primary population for all immunogenicity data analyses.

Modified intent-to-treat (mITT)	
All participants who receive 1 dose of the investigational product and have at least 1 valid and determinate assay result after receiving the investigational product. Participants will be summarized according to the investigational product group to which they were assigned.
 
The immunogenicity results based on the mITT population will be summarized for immunogenicity endpoints if there is a 10% or more difference between the mITT population and the evaluable immunogenicity population.

Safety	
All participants who receive 1 dose of the investigational product and have at least 1 safety assessment after receiving the investigational product. Participants will be summarized according to the investigational product they received.

Major protocol violations will be determined by clinical review (through the data handling memo). A major protocol violation is a protocol violation that, in the opinion of the clinician, would materially affect assessment of immunogenicity (eg, participant receipt of a prohibited vaccine or medication that might affect immune response or a medication error with suspected decrease in potency of the vaccine). The sponsor's clinician will identify those participants with protocol violations before any immunogenicity analysis is carried out.

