### 6.5.2. Study Conduct and Participant Disposition

The number and proportion of assigned participants will be included in the participant disposition summary. In addition, participants who completed each follow-up visit and withdrew before the follow-up visit, along with the reasons for withdrawal, will be tabulated

by vaccine group. The reasons for withdrawal will be those as specified in the database. Additionally, participants who missed at least 1 study procedure but continued in the study for safety follow-up will be summarized.

Participants excluded from the evaluable immunogenicity and mITT populations will also be summarized with reasons for exclusion.

The number and proportion of participants assigned, vaccinated, and who had blood drawn within the protocol-specified time frame and outside the specified window for all participants will be tabulated by vaccine group and the total sample.

The number and proportion of participants with e-diary data not transmitted, transmitted by day (Days 1-14), and transmitted all days will be summarized by vaccine group and the total sample.

Participant data listings of participants who withdrew during the study will be generated. Also, data listings for participants excluded from the evaluable immunogenicity and mITT populations will be generated separately.

The protocol deviation listings will be generated. In addition, participants who do not receive the vaccine as assigned will be listed.

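### Six SAP sections apply the evaluable-set deletion rule to the mITT analysis as well, and SAP 4.1 disagrees with Table 6 on who belongs to mITT

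*SAP*

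**What the plan says.** **Rule and populations.** SAP 6.2.1 gives its analysis populations as "Evaluable immunogenicity and mITT (provided there is a 10% or more difference with evaluable) populations". Its intercurrent-event bullet says that, for participants who discontinue or have a major violation, "no observations following discontinuation or violation will be used. Results obtained from out-of-window blood draws will also be removed". Nothing limits that bullet to one population. SAP 6.2.2, 6.2.5, 6.3.2, 6.3.3 and 6.3.6 have the same pairing.

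**Where the rule belongs.** SAP 2.1.4 gives the same rule under secondary estimands that each carry the line "Population: Evaluable immunogenicity analysis set as defined in" Table 6. Protocol 9.1.1 says that participants who discontinue or have a major deviation before Visit 2 "will be excluded from the evaluable population in the analysis".

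**Evaluable set (Table 6).** The Visit 2 draw must fall "within 27 to 45 days, inclusive, after vaccine administration", and participants must "Have no major protocol violation as determined by the study clinician". They must also be eligible and have received the vaccine assigned.

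**mITT (Table 6, protocol 9.3).** A member needs one dose and at least one valid post-dose assay result, and is summarised by assigned group. There is no window or violation criterion. mITT results are reported if the two populations differ by 10% or more.

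**Other statements on mITT.**
- SAP 4.1 puts assigned but unvaccinated participants with assay results in mITT. It admits wrong-vaccine recipients if they have any assay result, and it leaves out those vaccinated without an assignment.
- SAP 6.3.6 lists mITT, then says that participants from the evaluable populations of the two studies will be included.
- SAP 6.2.5 names mITT and refers to 6.4 for the strata. SAP 6.4 restricts the stratified GMCs to the evaluable population.

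**The concern.** The natural use of an mITT analysis beside an evaluable one is to show whether the evaluable exclusions change the GMCs and GMTs. A rule that removes from mITT the results that made people non-evaluable takes away much of that contrast. Agreement between the two tables could then come from the rule and be misread as robustness.

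The 10% trigger could also fire because of participants whose Visit 2 results are then discarded. Where their Day 1 results stay, the Day 1 and Visit 2 rows of one mITT table rest on different people.

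The membership conflict is separate. An undosed participant has no post-booster result. Including such a person adds at most Day 1 data and enlarges the mITT count on which the trigger depends.

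**Working it through.** **1. Tally.** Twelve SAP immunogenicity sections carry the rule. Six pair it with both populations (6.2.1, 6.2.2, 6.2.5, 6.3.2, 6.3.3, 6.3.6). Six are evaluable-only (6.2.3, 6.2.4, 6.3.1, 6.3.4, 6.3.5, 6.4).

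**2. What the rule can remove at Visit 2.** I crossed every draw day from 20 to 55 with violation status (none, before the draw, after it), eligibility and correct vaccine. I applied Table 6's evaluable criteria and then the rule.
- With a 27-45 day window, 0 evaluable profiles lose a Visit 2 result. Table 6 has already excluded out-of-window draws and all major violators, and protocol 9.1.1 excludes those who discontinue before Visit 2.
- Outside the evaluable set, a Visit 2 result survives only if the draw is in window and no major violation came before it. That leaves ineligible or wrong-vaccine participants without a prior major violation, and participants whose violation followed the draw. The collapse is therefore partial.
- This concerns Visit 2 of this study. In 6.3.6 the rule could also act on evaluable participants at C1091001 time points.

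**3. Window.** Days 27-45 are 45 - 27 + 1 = 19 days. The schedule's "28-38 Days After Visit 1" covers 38 - 28 + 1 = 11. The 8 days that differ are day 27 and days 39-45.

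**4. Trigger denominator.** The SAP does not state it. For an illustrative mITT of 297 (the C1091001 completers):
- of mITT: 0.10 × 297 = 29.7, so 30 exclusions;
- of evaluable: 27/(297 - 27) = 27/270 = 10%, so 27 exclusions.

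**5. Count example.** Assume 200 mITT members, of whom 20 are excluded only for window or for a major violation that falls after the Day 1 draw and before Visit 2. With an mITT denominator, 20/200 = 10%, so the trigger fires. Under the literal rule the mITT table has n = 200 at Day 1 and n = 180 at Visit 2, the same 180 as the evaluable table. With 297 and 30 exclusions, the counts are 297 and 267. A violation before the Day 1 draw would remove the Day 1 result too.

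**6. Effect on the GMC.** The documents give no exclusion rate, mix of reasons or GMC ratio, so all three inputs are assumed:
- f, the share of mITT excluded from evaluable: 10-20%;
- r, the GMC ratio of excluded to evaluable: 0.5-2;
- s, the share of the excluded whose Visit 2 result survives the rule: 0-1.

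Ratio of mITT to evaluable GMC:
- all observed data: r^f, giving 0.5^0.20 = 0.87 to 2^0.20 = 1.15;
- literal rule: r^(sf/(1 - f + sf)).

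Share of the log shift still shown: s/(1 - f + sf), which does not depend on r.

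| s | Ratio under literal rule | Share of log shift shown |
|---|---|---|
| 0 | 1.00 | 0% |
| 0.2 | 0.97-1.03 | 22-24% |
| 0.5 | 0.93-1.08 | 53-56% |
| 0.8 | 0.89-1.12 | 82-83% |
| 1 | 0.87-1.15 | 100% |

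For example, at s = 0.5 and f = 0.20 the share is 0.5/0.9 = 56%. At r = 1 there is no shift to hide.

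**7. Membership side by side.**

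| Group | SAP 4.1 | Table 6 wording |
|---|---|---|
| Assigned, not vaccinated | In mITT with a valid result | Out: no dose, no post-dose result |
| Wrong vaccine | In mITT with any result | In only with a valid post-dose result |
| Vaccinated, not assigned | Out | In, if a post-dose result exists |

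**The case against.** The rule is labelled as an intercurrent-event strategy, and SAP 2.1.4 ties that strategy to the evaluable set. The bullet looks copied into Section 6 without its population line, and a programmer may well apply it to the evaluable set alone. Table shells and programming rules are kept separately and may settle the matter. This makes unclear scope the likely cause. It does not settle the text: in 6.2.1 and 6.2.2 the bullet on distribution curves is expressly limited to the evaluable population, so the SAP writes a limiter when it wants one.

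The practical reach may be small. mITT is reported only if the trigger fires. People who stop blood draws stay only for safety follow-up, so the discontinuation limb should rarely matter. Undosed participants with serology should be few. Each table shows n, and exclusions are summarised and listed with reasons. All of this stands and limits the weight of the point.

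Four stronger readings are tempting, and the documents do not support them.
- *The mITT analysis always collapses into the evaluable one.* It does so only if every exclusion is of a kind that the rule also deletes.
- *SAP 6.3.6 contradicts Table 6's definition of mITT.* It does not define mITT. Its sentence may only describe how the evaluable sets are pooled, so this is an ambiguity within 6.3.6.
- *Out-of-window means 28-38 days, so evaluable results are deleted too.* SAP 6.5.2 does tabulate participants "who had blood drawn within the protocol-specified time frame and outside the specified window", but that is a disposition summary. Protocol 9.3 leaves the evaluable window open and Table 6 fills it with 27-45 days. The term still needs a definition.
- *The 10% trigger has a stated purpose that the rule defeats, or mITT would test the MCAR assumption.* The documents give the trigger without a purpose; its use as a check on the exclusions is inferred. The MCAR assumption concerns missing serology, which mITT does not test.

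**Conclusion.** The point holds as a defect of wording with real consequences if followed. Read literally with the 27-45 day window, the rule does nothing to evaluable Visit 2 results and strips from mITT many of those it would otherwise add. A triggered mITT table would partly or wholly repeat the evaluable table. SAP 4.1 departs from Table 6 in all three categories. The inclusion of undosed participants is a plain contradiction, also of protocol 9.3. SAP 6.2.5 and 6.4 disagree on whether mITT applies to the stratified GMCs.

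The size of any GMC effect is unknown, and the numerical ranges above rest entirely on assumed values. The unequal-n example further assumes violations after the Day 1 draw and an mITT denominator. The figure of 297 is illustrative: not all completers need enrol, and some who withdrew from C1091001 after the 1-month draw are eligible. The endpoints affected are secondary or other and descriptive. This is worth correcting but does not threaten the study's main conclusions.

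**What to change.** Change SAP wording only:
- In 6.2.1, 6.2.2, 6.2.5, 6.3.2, 6.3.3 and 6.3.6, limit the deletions to the evaluable analysis. State that mITT uses all valid results of its members, by assigned group. If the sponsor wants out-of-window draws kept out of mITT too, Table 6 should say so.
- Define out-of-window as outside Table 6's 27-45 days.
- Align all three categories in SAP 4.1 with Table 6 and protocol 9.3. If participants vaccinated without an assignment are to stay out because they have no assigned group, make assignment a condition in the mITT definition.
- Make 6.2.5 and 6.4 agree on mITT, and clarify the population sentence in 6.3.6.
- State the denominator of the 10% trigger.

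No visits, samples or assays are added. The cost is a few extra or changed tables if the trigger is met.

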#### **6.2.2. GBS Serotype-Specific OPA GMTs Before and 1 Month After Booster Vaccination**

- Analysis population: Evaluable immunogenicity and mITT (provided there is a 10% or more difference with evaluable) populations ([Section 4](#)).
- Analysis time point: Before and 1 month after vaccination.
- Analysis methodology: Descriptive summary statistics.
- Supporting objective: Secondary objective.
- Intercurrent event(s): For participants who discontinue or have major protocol violations, no observations following discontinuation or violation will be used. Results obtained from out-of-window blood draws will also be removed. Missing results will not be imputed.
- GMT of the OPA at each available time point for each serotype will be presented by vaccine group. For each vaccine group, the number of participants with valid assay data (n), GMTs, and associated 2-sided 95% CI will be presented.
- Figures of RCDCs for 1 month after the vaccination time point will be generated separately for each serotype by vaccine group. The figures will be based on the evaluable immunogenicity population only.

### **6.2.3. GBS Serotype-Specific IgG GMFRs From Before to 1 Month After Booster Vaccination**

- Analysis population: Evaluable immunogenicity population ([Section 4](#)).
- Analysis time points: Day 1 and 1 month after booster vaccination.
- Analysis methodology: Descriptive summary statistics.
- Supporting objective: Secondary objective.
- Intercurrent event(s): For participants who discontinue or have major protocol violations, no observations following discontinuation or violation will be used. Results obtained from out-of-window blood draws will also be removed. Missing results will not be imputed.
- The number of participants with valid assay data (n), GMFRs of IgG, and associated 2-sided 95% CIs will be presented for each serotype by vaccine group.

### **6.2.4. GBS Serotype-Specific OPA GMFRs From Before to 1 Month After Booster Vaccination**

- Analysis population: Evaluable immunogenicity population ([Section 4](#)).
- Analysis time points: Day 1 and 1 month after booster vaccination.
- Analysis methodology: Descriptive summary statistics.
- Supporting objective: Secondary objective.
- Intercurrent event(s): For participants who discontinue or have major protocol violations, no observations following discontinuation or violation will be used. Results obtained from out-of-window blood draws will also be removed. Missing results will not be imputed.
- The number of participants with valid assay data (n), GMFRs of OPA, and associated 2-sided 95% CIs will be presented for each serotype by vaccine group.

### **6.2.5. GBS Serotype-Specific IgG GMCs Measured 1 Month After Booster Vaccination Stratified by Baseline GBS Prevaccination Status (Before the Primary Vaccination)**

- Analysis population: Evaluable immunogenicity and mITT (provided there is a 10% or more difference with evaluable) populations ([Section 4](#)).
- Analysis time point: Before and 1 month after booster vaccination.
- Analysis methodology: Descriptive summary statistics.

- Supporting objective: Secondary objective.
- Intercurrent event(s): For participants who discontinue or have major protocol violations, no observations following discontinuation or violation will be used. Results obtained from out-of-window blood draws will also be removed. Missing results will not be imputed.
- GMC of the IgG at each available time point for each serotype by baseline GBS prevaccination status will be presented by vaccine group. For each vaccine group, the number of participants with valid assay data (n), GMCs, and associated 2-sided 95% CI will be presented.

For details of baseline GBS prevaccination status and other baseline variables of interest, refer to [Section 6.4](#).

